11.4.4 Interim Analyses

Two interim analyses after 32 and 80 patients are planned according to the Pocock adjusted levels $\alpha_p = 0.0221$. Based on the results of an interim analysis the sample size can be adjusted (Lehmacher, Wassmer, 1999). There are no prespecified futility margins, but the DSMB can recommend stopping the study in the case of insufficient interim results.

11.4.5 Safety Analysis

The assessment of safety will be based mainly on the frequency of adverse events (AEs) that are treatment-emergent (TEAEs). Formal tests will not be conducted for differences in safety parameters between treatment groups.

The incidence of all treatment-emergent AEs will be tabulated after grouping by system organ class and preferred term. For each preferred term and summarized over each system organ class overall, the table will present the absolute number and proportion (%) of patients in each treatment group in whom the event occurred. The incidence of all suspected-IMP-related AEs will be tabulated similarly. The incidence of all treatment-emergent AEs will also be tabulated by severity categories.

Safety will also be summarized with respect to vital signs as mean levels by visit and change from baseline. Abnormal observations on physical exams will be listed.

11.4.6 Deviation(s) From the Original Statistical Plan

Deviations from the planned analyses will be discussed by the Sponsor and the biostatistician and consequently justified and reported in the final reports and the publications.

11.5 Handling of Missing Data and Drop-Outs

Withdrawn/discontinued participants will not be replaced. Missing data for the primary variable will be imputed by means of the Last-observation-carried forward (LOCF) method, as sensitivity analyses some alternative imputation methods like imputation of the mean and multiple imputation will be additionally performed.

12. QUALITY ASSURANCE AND CONTROL

The Sponsor and the local site Investigators are responsible for proper training of all involved study personnel and for implementing and maintaining quality assurance and quality controls systems with written SOPs and working instructions. All SOPs and working instructions will be prepared and critically evaluated by the Investigators and study nurses and monitors before commencement of the trial.

12.1 Data Handling and Record Keeping / Archiving

12.1.1 Case Report Forms

Study data will be recorded in a Case Report Form (CRF). A unique study code will be used for identification of participants in the CRF. Subjects will not be identified in the CRF by name or date of birth. Only authorized personnel will be able to make changes on the paper case report form (CRF) and are responsible for entering complete data. If source data is available as a print-out (e.g. laboratory values), this print-out will be kept on file in a source data folder, and the data necessary for the study is to be added to the CRF immediately.

12.1.2 Specification of Source Documents

Source data include the paper and electronic records of the hospitals at the respective study sites and all study documents (AE/SAE form, informed consent forms, laboratory reports etc.). Source data includes demographic data, visit dates, informed consent forms, randomization numbers, SAEs, AEs, concomitant medication, results of physical examination and information related to COVID-19 infection (e.g. data from viral sampling). Source data may be found either in the electronic or paper-based records of the hospitals at the respective study sites or as a print-out of study-related laboratory results which will be mailed to the local Investigators from the central laboratory hospitals at the respective study sites.

12.1.3 Record Keeping / Archiving

All study data will be archived for a minimum of 10 years after study termination or premature termination of the clinical trial.

12.1.4 Data Management System

The clinical trial data will be collected in a secure, validated EDC system.

12.1.5 Analysis and archiving

The EDC will be locked after all data was monitored and all raised queries have been resolved. Data is exported and transferred to the sponsor-Investigator by the CTU according to internally defined processes. Data will be archived by the by the Investigators as described above.

12.2 Monitoring

Monitoring will be carried out according to a predefined monitoring plan by Pharming (Sponsor), which is independent from the Investigators. Study documentation and all source data/documents will be accessible to monitors and all questions will be answered during inspections. Participants' data will be kept strictly confidential during the monitoring visits.

12.3 Audits and Inspections

Audits may be conducted by the IRBs and FDA and are independent from Investigators. Study documentation and all source data/documents will be accessible to auditors/inspectors and all questions will be answered during inspections. Participants' data will be kept strictly confidential during the monitoring visits. The Investigator should contact the Sponsor immediately if this occurs and must permit regulatory authority inspections.

12.4 Protocol Deviations

This study will be conducted as described in this protocol, except for an emergency situation in which the protection, safety, and well-being of the subject requires immediate intervention, based on the judgment of the Investigator (or a responsible, appropriately trained professional designated by the Investigator). In the event of a significant deviation from the protocol due to an emergency, accident, or mistake, the Investigator or designee must contact the Sponsor, or their agent, at the earliest possible time by telephone. This will allow an early joint decision

regarding the subject's continuation in the study. The Investigator and the Sponsor will document this decision. The IRB will be informed of all protocol changes by the Investigator in accordance with the IRB established procedure. No deviations from the protocol of any type will be made without complying with all the IRB established procedures.

Any protocol deviations that will affect the subject's safety or the study objectives may be considered Major Protocol Deviations upon review by the Sponsor. In addition, the following will be classified as Major Protocol Deviations:

- Inclusion/Exclusion Criteria
- Informed Consent not properly obtained
- Study Drug dosing variation
- SAE not reported in a timely manner

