10.1.2 Reporting of Serious Adverse Events (SAE) and Other Safety Related Events

Reporting of SAEs

All SAEs must be reported immediately and within a maximum of 24 hours to the Sponsor via email at [contact] or fax at 1 [contact].

Reporting of SUSARs

Fatal or life-threatening SUSARs need to be reported to the IRB and to Competent Authorities (e.g. FDA and EMA) within 7 calendar days. Follow-up information to Fatal or life-threatening SUSARs or other SUSARs need to be reported within 15 calendar days.

The Sponsor must inform all Investigators participating in the clinical study of the occurrence of a SUSAR.

Reporting and Handling of Pregnancies

In case a patient becomes pregnant during the study, the patient should be withdrawn immediately from the study. Any pregnancy during the treatment phase of the study and within 30 days after discontinuation of study medication will be reported to the Sponsor and within a maximum of 24 hours to the Sponsor. The course and outcome of the pregnancy should be followed up carefully, and any abnormal outcome regarding the mother or the child should be documented and reported to the Sponsor following the SAE reporting timelines.

Reporting of Special Situations

All special situations must be reported as an SAE within 24 hours of the Investigator's first knowledge of the event, even if considered non-serious and regardless or not of whether an (S)AE occurred.

Special situations may include, but are not limited to, the following:

- Use of a medicinal product during pregnancy or breastfeeding
- Use of a medicinal product in a pediatric or elderly population
- Reports of overdose, abuse, off-label use, misuse, medication error or occupational exposure
- Lack of therapeutic efficacy
- (Suspected) transmission of an infectious agent

Overdose

For this study any dose of rhC1INH greater than 100 U/kg will be considered an overdose.

Medication errors

A medication error is any unintentional error in the prescribing, dispensing, or administration of a medicinal product while in the control of the healthcare professional or patient. Examples of medication error include, but are not limited to: wrong dose, wrong or inadequate (route of) administration, equipment failure, preparation error. Medication errors are reported in the CRF. A description of the error must be provided and whether or not the medication error lead to any AE.

Periodic Reporting of Safety

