11.4 Planned Analyses

11.4.1 Datasets to be Analysed, Analysis Populations

A review of the database will be conducted in a blinded manner shortly before the database will be locked, and any decisions made at that meeting (blinded Data Review Meeting) concerning the statistical analysis, e.g., additional outcomes and populations, pooling of sites for efficacy analysis, will be documented in the Statistical Analysis Plan (SAP).

Missing data for the primary endpoint will be imputed by means of the Last-observation-carried-forward (LOCF) method, as sensitivity analyses some alternative imputation methods like imputation of the mean and multiple imputation will be additionally performed.

Safety Population: The Safety Population is defined as all patients who received at least one dose of rhC1INH. Statistical analyses will be based on the actual treatment the patient received.

Full Analysis Set/Intent-to-Treat Population: The FAS/ITT Population is defined as all patients who are randomly allocated to a study arm. Statistical analyses will be based on the treatment arm to which the patient was allocated. For quantitative data, the number of patients with non-missing information, means, medians, standard deviations and extremes will be determined. For qualitative data, absolute and relative frequencies will be calculated. Moreover, changes from baseline (V2, d0) will be calculated.

Per Protocol Population: The PP Population is defined as all patients in the FAS/ITT Population who complete the study and who do not have any major protocol violations, including the following:

- Patients who had major inclusion/exclusion criteria violations.

Sufficient compliance is expected because of IV administration of the IMP.

The PP Population will be determined by a blinded review in the Data Review Meeting (DRM) of the data prior to database lock. The primary efficacy analysis will be based on the FAS/ITT Population in this superiority trial; an additional efficacy analysis will be performed on the PP Population. The Safety Population will be used for all safety analyses.

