12 BLIND REVIEW

A blind data review meeting will take place before closing the database. A listing of all protocol deviations with the proposed classification into minor and major protocol deviations and a list of all data irregularities or unresolved queries and a proposal for how the data are to be handled in the analysis, if necessary, will be provided in the Blind Review Meeting (BRM). At least the responsible biometrician and the Clinical Project Manager will sign the Blind Review Meeting Minutes.

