14.2 Datasets to be analyzed, Analysis populations

A review of the database will be conducted in a blinded manner shortly before the database will be locked, and any decisions made at that meeting (blinded Data Review Meeting) concerning the statistical analysis, *e.g.*, additional outcomes and populations, pooling of sites for efficacy analysis, will be documented in the Statistical Analysis Plan (SAP).

Missing data for the primary endpoint will be imputed by means of the Last-observation-carried-forward (LOCF) method, as sensitivity analyses some alternative imputation methods like imputation of the mean and multiple imputation will be additionally performed.

The following analysis populations will be used for analysis of study data:

Safety population: The Safety Population is defined as all patients who received at least one dose of rhC1-INH. Statistical analyses will be based on the actual treatment the patient received.

Full Analysis Set (FAS)/Intention to treat (ITT) population: The FAS/ITT Population is defined as all patients who are randomly allocated to a study arm. Statistical analyses will be based on the treatment arm to which the patient was allocated. For quantitative data, the number of patients with non-missing information, means, medians, standard deviations and extremes will be determined. For qualitative data, absolute and relative frequencies will be calculated. Moreover, changes from baseline (V2, d0) will be calculated.

Per protocol (PP) population: The PP Population is defined as all patients in the FAS/ITT Population who complete the study and who do not have any major protocol violations, including the following:

- Patients who had major inclusion/exclusion criteria violations.

Sufficient compliance is expected because of IV administration of the IMP.

The PP Population will be determined by a blinded review in the Data Review Meeting (DRM) of the data prior to database lock. The primary efficacy analysis will be based on the FAS/ITT Population in this superiority trial; an additional efficacy analysis will be performed on the PP Population. The Safety Population will be used for all safety analyses.

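### A site's late SAE report can remove a patient from the per-protocol set, which ties PP membership partly to outcome; the direction of any bias is not fixed and its size is probably small

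*Protocol*

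**What the plan says.** Protocol 12.4 first allows the sponsor to judge whether a deviation affecting safety or study objectives is major. It then adds a fixed list of four items: "In addition, the following will be classified as Major Protocol Deviations". One of the four is "SAE not reported in a timely manner". The deadline comes from Protocol 10.1.2: "All SAEs must be reported immediately and within a maximum of 24 hours to the Sponsor".

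Protocol 11.4.1 defines the PP population as FAS/ITT patients "who complete the study and who do not have any major protocol violations, including the following", and SAP 14.2 uses the same definition. One example follows: "Patients who had major inclusion/exclusion criteria violations". Neither document limits PP exclusions to deviations that bear on efficacy, and neither exempts reporting failures.

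On procedure, SAP 14.2 states: "The PP Population will be determined by a blinded review in the Data Review Meeting (DRM) of the data prior to database lock". SAP 12 has the meeting receive "A listing of all protocol deviations with the proposed classification into minor and major protocol deviations". Both documents make FAS/ITT primary and PP an additional efficacy analysis.

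**The concern.** Meeting the 24-hour deadline is the site's duty. Missing it says nothing about whether the patient was eligible, was treated as assigned, or had a valid Day-7 score. Yet this deviation can arise only in a patient who had an event reportable as an SAE. The SAE criteria in Protocol 10.1.1 include death and prolonged hospitalization, while the WHO scale in Protocol 5.1 scores death as 7 and continued hospitalization as 3 to 6. Removal from PP therefore depends on a post-randomization event that overlaps the endpoint.

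The PP analysis is meant to show whether the primary result holds among patients who followed the protocol. If it differs from the FAS/ITT result because of late paperwork, the difference would be misread as saying something about adherence or eligibility.

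**Working it through.** **The plan's own figure.** The point contradicts no stated number, but the planned effect of 1 point and SD of 1.5 (Protocol 11.2) give the scale. The normal approximation is 2 × (1.960 + 0.842)² × 1.5² / 1² = 35.3, so 36 per arm; the t-test gives 37. The stated 38 is consistent with these.

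**Step 1: the textual chain.** A late SAE report is a major deviation with no discretion (12.4). Any major violation excludes from PP (11.4.1, SAP 14.2). The eligibility bullet is introduced as an example, not as the complete list. The link needs *violation* to mean *deviation*.

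**Step 2: formula.** Let p be the SAE rate in an arm, l the share of SAE patients whose report is late, mS the mean Day-7 score of SAE patients and m the arm mean. Removing the late-reported patients moves the arm mean by

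−p·l·(mS − m) / (1 − p·l).

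The PP effect is the control mean minus the rhC1INH mean after removal. I use a mean difference because the plan states its effect in points.

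**Step 3: inputs.** From the documents: 80 v 40 patients and a 1-point effect. Assumed: arm means 4.0 (control) and 3.0 (rhC1INH), mS = 6, control SAE rate 20%, late share 10–30%. Protocol 3.8 puts progression to severe lung injury at 15–20%, which is only a stand-in for the control SAE rate. The documents give no SAE or late-report rate by arm.

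**Step 4: equal late share in both arms.** Worked case, 20% v 10% SAE rates and 20% late:
- Control: −0.04 × 2 / 0.96 = −0.083.
- rhC1INH: −0.02 × 3 / 0.98 = −0.061.
- PP effect: 1 − 0.083 + 0.061 = 0.98.
- Expected removals: 40 × 0.20 × 0.20 = 1.6 control and 80 × 0.10 × 0.20 = 1.6 rhC1INH.

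PP effect against a true 1.00:

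| rhC1INH SAE rate | 10% late | 20% late | 30% late |
|---|---|---|---|
| 5% | 0.97 | 0.95 | 0.92 |
| 10% | 0.99 | 0.98 | 0.97 |
| 15% | 1.00 | 1.01 | 1.01 |
| 20% | 1.02 | 1.04 | 1.06 |

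The sign changes at an rhC1INH SAE rate of about 13–14% (about 10% if mS = 5, about 15% if mS = 7).

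**Step 5: unequal late share.** With SAE rates 20% v 10%:
- 30% late in control and 10% in rhC1INH gives 1 − 0.128 + 0.030 = 0.90.
- 10% late in control and 30% in rhC1INH gives 1 − 0.041 + 0.093 = 1.05.

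With no true effect (common mean 3.5, SAE rate 20% in both arms), 10% late in control v 30% in rhC1INH gives −0.051 + 0.160 = +0.11; reversing the shares gives −0.11. Over all cases run with mS of 5 or 6, equal and unequal, the PP effect ranged from 0.85 to 1.15 against 1.00.

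**Step 6: all benefit comes from preventing severe events.** Suppose patients without a severe event have the same mean score in both arms. The effect is then proportional to the difference in severe-event rates, and each rate becomes p(1 − l)/(1 − p·l) after removal. For 20% v 10%:
- 10% late: 0.1837 − 0.0909 = 0.0928, a 7% loss.
- 20% late: 0.1667 − 0.0816 = 0.0850, a 15% loss.
- 30% late: 0.1489 − 0.0722 = 0.0768, a 23% loss.

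If severe and other patients differ by 3 points on average (assumed), the full-set effect is only 0.10 × 3 = 0.30 points, and it falls to 0.28, 0.26 and 0.23. The proportional loss is larger than in Step 4, but the absolute change (0.02 to 0.07 points) is similar.

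**The case against.** The strongest reply is that the rule may never operate. The documents do not equate *violation* in the PP definition with *deviation* in 12.4, eligibility violations are the only kind named for PP, and a blinded meeting settles both classification and membership. PP is an additional analysis, and its completion requirement may already exclude deaths.

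Part of this stands. The link is an inference, and the reach is limited to a secondary analysis. But 12.4 has already fixed this item as major, and a meeting blind to arm would still be applying an outcome-related rule. A ventilated survivor who completes follow-up passes the completion requirement and could still be removed for a late report.

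A reader might infer that only patients with serious outcomes can be removed. The documents do not support that. Protocol 10.1.2 also requires special situations, including medication errors and lack of efficacy, to be reported as SAEs even when non-serious. Adverse events are collected for 3 months (Protocol 9.1.4.1), so a late-reported SAE may fall long after Day 7. The link with the Day-7 score is therefore partial, and Step 6, which ties removal entirely to severe events, overstates it.

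**Conclusion.** The point holds as a minor defect in the PP definition. On the natural reading, a site's reporting delay excludes a patient for a reason unrelated to eligibility, treatment or measurement, and only patients with an SAE-reportable event are exposed to it.

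A reader might go further and infer that the PP estimate must shrink. That does not follow. It shrinks if the drug mainly prevents severe events and late reporting is equal by arm. With similar SAE rates it can grow. With unequal late reporting, which is possible because site staff are not blinded (Protocol 6.2.2), it can move either way.

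The size is probably small. In the equal-late-share cases of Step 4, a 1-point effect changes by about 0–8% in either direction, with a few patients removed. A larger proportional loss arises if the whole benefit comes through severe events, but from a much smaller effect than the plan assumes. All of this rests on assumed SAE rates, late shares and score means. The primary FAS/ITT analysis is unaffected.

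**What to change.** In SAP 14.2 and Protocol 11.4.1, state that exclusion from PP uses only deviations that affect eligibility, treatment received or the Day-7 measurement. Add that late SAE reporting remains a major deviation under Protocol 12.4 but does not exclude a patient from PP. The same sentence should say how *violation* in the PP definition relates to *deviation* in 12.4.

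With this change the rule removes no patients from PP, so this source of bias is zero whichever direction it would have taken. The cost is a sentence or two in each document, settled before the data review meeting. It needs no new data and does not change the primary analysis.

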12.5 Confidentiality, Data Protection

All staff involved in the study is obliged to follow the ICH-GCP regulations, local requirements and privacy policy. Data will be archived. Any hard copies of the source documentation will be maintained in a locked filing cabinet with limited access. Subject confidentiality will be maintained throughout the clinical study in a way that ensures the information can always be tracked back to the source data. For this purpose, a unique subject identification code will be used that allows identification of all data reported for each subject.

Blood samples will be de-identified, labelled with a unique study code. Samples will be destroyed 10 years after study termination. Data and samples will be accessible only to authorized staff for scientific purposes. Throughout the study and during aforementioned inspections, strict confidentiality is guaranteed. In any publication and/or presentation, information will be provided in such a way that the participants cannot be identified, except with their permission and individual patient data will not be shown. Direct access to source documents will be permitted for the purpose of monitoring, audits and inspections by respective authorities.

12.6 Storage of Biological Material and Related Health Data

Blood and urine samples will be stored at -80°C in a dedicated freezer with limited access to unauthorized personal. The same applies to study data, which will be stored in a password secured database, and maintained by qualified IT specialists. All data including samples and source data (patients' charts) are stored for ten years.

13. PUBLICATION AND DISSEMINATION POLICY

Data derived from this clinical trial is considered to be the property of Pharming Technologies B.V. (the Sponsor). Study results will be presented at national and international conferences and published in peer reviewed medical journals. Trial results will be disseminated to the public and patients through publications in national and international journals, presentations at conferences and through publication of results in a public registry.

As a multicenter study, the first publication is intended to be a multicenter publication of the results of the overall study. In these cases, the Sponsor will be responsible for these activities and will work with the Investigators to determine how the manuscript is written and edited, the number and order of authors, the publishing journal/newsletter to which it will be submitted, and other related issues. The contributions of any contributor to the project will be taken into account in a fair and collegial way. Persons qualify for authorship if they have contributed significantly to the trial. The last author of the main publication will be the Principal Investigator, [name]. If a contributor will not qualify for authorship, her/his contribution will be mentioned as an acknowledgment.

Any individual publications, presentations or other disclosures of any study results by the centers or the local Investigator shall require the Sponsor's written consent and shall not occur until after the multicenter publication is published, which is intended to occur within 12 months after completion of the study at all study sites and lock of the database at all study sites.

All proposed publications are to be provided to Pharming a minimum of 60 days before submission to prospectively review any proposed publication, abstract, other type of disclosure that reports the results of the study. Pharming may wish to disclose results of the study after publication/presentation.

All financial support will be disclosed in any publication of study results.

In accordance with national and local requirements, this study will be listed in a publicly accessible clinical studies registry and be given a unique identifier (e.g. ClinicalTrials.gov). Additionally, the results of this study will be disclosed on a publicly accessible clinical studies results database, regardless of the outcome.

